12.5 Efficacy analysis listings

Listings: It be provided a listing with date of visit, visit type (baseline, follow-up month), eye (Left/Right), logMAR VA at the visit, logMAR VA at baseline, difference in logMAR VA at the visit compared with baseline, CRR, CRS, CRB, CRW, order by center, patient identification and date of visit.

13 Analysis of safety and tolerability

In CRS-1 and CRS-2 no safety information was collected.

The safety data of LEROS, as available, will be analysed using the Safety population.

13.1 Extent of exposure

The following information will be summarized from the Safety population:

- Total exposure to study treatment, expressed as person years (sum of duration of exposure to study treatment over all patients in days divided by 365.25)
- Average exposure: duration of exposure in days summarized using the number of observations (n), mean, standard deviation (SD), median, 1st and 3rd quartile, minimum and maximum
- Cumulative overall exposure: cumulative number and proportion of patients treated as tabulated in Table 13-1.

Table 13-1 - Extent of exposure: cumulative number and proportion of patients in the Safety population

	1 day	> 3 months	> 6 months	> 9 months	> 12 months	> 18 months	> 24 months
N	Xx	xx	xx	Xx	Xx	xx	xx
%	xx.x	xx.x	хх.х	xx.x	xx.x	xx.x	xx.x

Duration of exposure (days) is defined as: date of last dose of study medication - date of first dose of study medication +1.

13.2 Compliance

Treatment compliance will be calculated as percentage by dividing the number of tablets taken (tablets dispensed less tablets returned) by the number of days since the Raxone/idebenone first intake to Raxone/idebenone last intake multiplied by six and divided by 100.

For patients being compliant the calculated percentage must lie within the range of 80-120% (inclusively).

SNT-IV-005 Statistical Analysis Plan

Confidential

The number and proportion of patients who are compliant or non-compliant to the study treatment, as well treatment overall compliance as described in Table 13-2. In addition, the total number and proportion of patients who were non-compliant at least once during the study will be tabulated.

Table 13-2 LEROS medication compliance

Compliance as derived from eCRF	
Overall compliance, N mean (SD ; SE) median ($Q_1 - Q_3$) min-max	xx xx.xx (xx.xx ; xx.xx) xx.xx (xx.xx – xx.xx) xx.xx – xx.xx
Visit cumulative overall exposure, n(%)	
Yes (compliance 80%-120%)	xx (xx.x%)
No (compliance < 80%)	xx (xx.x%)

Listings: It be provided a listing with date of visit, visit type (baseline, follow-up month or unscheduled), start date of treatment, stop date of treatment, number of tablets dispensed, number of tablets returned, compliance, order by center, patient identification and date of visit.

13.3 Adverse events

In CRS-1 and CRS-2 no adverse events information was collected.

All adverse events (AEs) of patients participating in LEROS will be coded using most recent MedDRA version.

The treatment-emergent AEs (i.e., events which start or worsen during the study treatment) will be tabulated by system organ class (SOC) and preferred term (PT). Both subject and event counts will be calculated as described in Table 13-3.

Table 13-3 – AE by SOC and PT

	Events	Patients	Rate	Days in Ti	reatment ¹
				mean (SD)	min – max
Total patients with AE	xx	xx	xx.x	xx.x (xx.x)	xx.x – xx.x
SOC - PT	xx (xx.x%) xx (xx.x%)	xx (xx.x%) xx (xx.x%)	xx.x xx.x	xx.x (xx.x) xx.x (xx.x)	xx.x – xx.x xx.x – xx.x

Days since start of treatment at the time of event

SNT-IV-005 Statistical Analysis Plan

Confidential

V1.0 07 June 2021

In addition, the treatment-emergent AEs will be evaluated by severity and by relationship to the study treatment. The serious AEs and AEs leading to a premature discontinuation will also be summarized as described in Table 13-4.

Table 13-4 - AE

	Events	Patients	Rate	Days in Tr	reatment ¹
				mean (SD)	min – max
AE	Xx	xx	xx.x	xx.x (xx.x)	xx.x – xx.x
Mild	xx (xx.x%)	xx (xx.x%)	хх.х	xx.x (xx.x)	xx.x – xx.x
Moderate	xx (xx.x%)	xx (xx.x%)	xx.x	xx.x (xx.x)	xx.x – xx.x
Severe	xx (xx.x%)	xx (xx.x%)	xx.x	xx.x (xx.x)	xx.x – xx.x
SAE	хх	xx	xx.x	xx.x (xx.x)	xx.x – xx.x
AESI	хх	xx	xx.x	xx.x (xx.x)	xx.x – xx.x

Days since start of treatment at the time of event

TEAEs are defined as all AEs that start after the patient receives the first dose of study treatment.

The incidence (number and % of patients), frequency (number of events) and rate (incidence/frequency) following summaries will be provided:

- TEAE as displayed in Table 13-5.
- TEAEs broken down by PT, sorted in descending order of PT.
- TEAEs broken down by SOC and PT.
- TEAEs broken down by SOC, PT and severity. This summary will be done for the event count only and % will be calculated out of the total number of TEAEs.
- TEAEs broken down by SOC, PT and relationship to study medication. This summary will be done for the
 event count only and % will be calculated out of the total number of TEAEs.
- TEAEs leading to death broken down by SOC and PT.
- TEAEs other than those leading to death broken down by SOC and PT.
- TEAEs leading to permanent discontinuation broken down by SOC and PT.
- TEAEs leading to temporary drug interruption broken down by SOC and PT.

SNT-IV-005 Statistical Analysis Plan

V1.0 07 June 2021

Confidential

Table 13-5 - TEAE

	Events	Patients	Rate	Days in T	reatment ¹
				mean (SD)	min – max
TEAE	хх	xx	хх.х	xx.x (xx.x)	xx.x - xx.x
Drug-related	xx (xx.x%)	xx (xx.x%)	xx.x	xx.x (xx.x)	xx.x - xx.x
Severe ²	xx (xx.x%)	xx (xx.x%)	xx.x	xx.x (xx.x)	xx.x - xx.x
Serious ²	xx (xx.x%)	xx (xx.x%)	xx.x	xx.x (xx.x)	xx.x – xx.x
leading to permanent study treatment discontinuation	xx (xx.x%)	xx (xx.x%)	хх.х	xx.x (xx.x)	xx.x – xx.x
leading to temporary dose interruption	xx (xx.x%)	xx (xx.x%)	xx.x	xx.x (xx.x)	xx.x – xx.x
leading to death	xx (xx.x%)	xx (xx.x%)	xx.x	xx.x (xx.x)	xx.x - xx.x

¹ Days since start of treatment at the time of event; ² Other than death

Unless stated otherwise, the tables will be sorted by alphabetical order of the SOCs and then, within each SOC, by overall descending frequency of PTs based on the patient count. If only event count is presented, the sorting will be done based on the event count.

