idebenone therapy and CRR, where possible compared to untreated control patients.

The treatment duration in RHODOS was 6 months and a larger proportion of idebenone-treated patients presented with CRR in VA compared to placebo. However, data from Santhera's ongoing Expanded Access Program (EAP) indicates that prolonged treatment can increase both the proportions of patients with CRR of VA and the magnitude of the recovery observed. Furthermore, data from the RHODOS and from the EAP provide evidence that the LHON-causative mutation harboured is prognostic of CRR in VA. Therefore, secondary objectives of this study are to provide information on the effect of treatment duration on both the proportions of patients presenting with CRR and on the magnitude of any response with increasing treatment time and on the influence of the mutation harboured on CRR rate compared to spontaneous CRR (sCRR) in untreated control patients.

The study will also allow the assessment of the safety and tolerability of long-term treatment with idebenone, with particular emphasis on the proportion of patients experiencing elevated Liver Function Tests (LFTs) or changes in blood cell counts.

Number of Centres

Approximately 35

Multinational study with US sites operating under IND and EU sites not operating under IND.

Number of Patients

80 patients presenting ≤1 year after the onset of symptoms will be enrolled to ensure 61 provide VA assessments following 12 months of idebenone treatment (primary endpoint).

80 patients presenting >1 year after the onset of symptoms will be enrolled to ensure 61 provide VA assessments following 12 months of idebenone treatment (secondary endpoint). Patients will be stratified according to time since onset of symptoms with a maximum of 30 patients to be enrolled in any of the strata of >1 - \leq 2 years, >2 - \leq 3 years, >3 - \leq 4 years and >4 - \leq 5 years since onset of symptoms.

Inclusion Criteria

- 1. Impaired visual acuity in affected eyes due to LHON
- 2. No explanation for visual loss besides LHON
- 3. Age \geq 12 years
- 4. Onset of symptoms ≤5 years prior to Baseline
- 5. Confirmation of either G11778A, G3460A or T14484C LHON mtDNA (for the ITT population, not required for enrolment)
- 6. Written informed consent obtained from the patient
- 7. Ability and willingness to comply with study procedures and visits

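### The SAP defines the adverse-event rate as patients divided by events, so the Rate column measures neither incidence nor event burden

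*SAP*

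**What the plan says.** SAP 13.3 introduces its list of treatment-emergent adverse event (TEAE) summaries with "The incidence (number and % of patients), frequency (number of events) and rate (incidence/frequency) following summaries will be provided". Incidence is thus tied to patients, frequency to events, and rate to the first over the second. Neither document defines the rate in any other way.

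A Rate column appears in Tables 13-3, 13-4 and 13-5. Separate columns hold the counts; for the system organ class and preferred term table, SAP 13.3 states "Both subject and event counts will be calculated as described in Table 13-3". Table 13-6 in SAP 13.4 repeats the Rate heading for clinically significant laboratory values, and that section does not say how it is calculated.

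SAP 13.1 plans "Total exposure to study treatment, expressed as person years", with each patient's exposure running from first to last dose. SAP 13.3 and 13.4 make no use of this total. Protocol 9.4.3 asks for subject counts, event counts and a summary of exposure, and defines no adverse-event rate.

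**The concern.** A column headed Rate in a safety table will be taken as a measure of how often something happens, either per patient or per unit of time at risk. Patients over events is neither. It rewards recurrence with a lower number and gives the same value to a rare single event and a common single event.

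Long-term safety is a stated objective, treatment is planned for 24 months, and the sample-size section allows for 30% drop-out, so time at risk will differ between patients. Protocol 8.1.2 singles out abnormal liver tests and blood counts, and blood is tested at every visit, so repeated findings in one patient are a realistic case. A programmer following the SAP exactly would print a figure that moves the wrong way for such findings.

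**Working it through.** The documents give no numerical adverse-event rate, so there is nothing to reproduce. The check applies the SAP formula to hypothetical counts.

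**Inputs**
- P = patients with the event and E = number of events (hypothetical).
- SAP rate = incidence / frequency, from SAP 13.3. On counts this is P/E. If incidence is read as a percentage, it is (100 × P/N)/E.
- N = 160, for illustration only. The Protocol synopsis states "80 patients presenting ≤1 year after the onset of symptoms will be enrolled" and "80 patients presenting >1 year after the onset of symptoms will be enrolled"; 80 + 80 = 160.
- Person-years (PY), assumed: 160 × 2 = 320 if everyone completes 24 months, and half of that, 160, as a low case.

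**Step 1, the bound.** Every affected patient has at least one event, so E ≥ P and P/E ≤ 1, with equality exactly when each affected patient has one event.

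**Step 2, the numbers.**

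| P | E | P/N | SAP rate, P/E | SAP rate, % / E | E/P | E per 100 PY (320 PY) | E per 100 PY (160 PY) |
|---|---|---|---|---|---|---|---|
| 1 | 1 | 0.6% | 1.00 | 0.625 | 1 | 0.31 | 0.62 |
| 10 | 10 | 6.25% | 1.00 | 0.625 | 1 | 3.1 | 6.25 |
| 10 | 20 | 6.25% | 0.50 | 0.312 | 2 | 6.25 | 12.5 |
| 10 | 40 | 6.25% | 0.25 | 0.156 | 4 | 12.5 | 25 |
| 80 | 80 | 50% | 1.00 | 0.625 | 1 | 25 | 50 |
| 80 | 320 | 50% | 0.25 | 0.156 | 4 | 100 | 200 |

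**Step 3, recurrence.** With 10 affected patients, going from 10 to 40 events multiplies the burden by 4 and cuts the SAP rate from 1.00 to 0.25.

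**Step 4, spread.** With one event each, 1, 10 and 80 affected patients all give 1.00, while incidence runs from 0.6% to 50%.

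**Step 5, the percentage reading.** (100 × P/N)/E = (100/N) × (P/E), which is the same quantity multiplied by 100/160 = 0.625. The ceiling becomes 0.625 instead of 1; the behaviour does not change.

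**Step 6, exposure.** Halving person-years from 320 to 160 doubles events per 100 person-years and leaves the SAP rate where it was.

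**Step 7, print format.** The shells show one decimal, so on counts the column can display only values from 0.0 to 1.0. That suggests an inverted fraction or a missing exposure denominator, but the SAP does not say which was meant.

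**The case against.** The strongest reply is that little is lost. Event and patient counts stand beside the rate, with percentages on most rows, so incidence is reported and anyone can invert the ratio. Safety is descriptive and covers treated patients only; the case record surveys collected no safety data, so there is no between-group comparison to distort. The Protocol never promised an exposure-adjusted rate. All of this stands, and it limits the point to one column.

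Three stronger readings are tempting and should not be drawn:
- *That the tables would place the most recurrent events last.* SAP 13.3 sorts preferred terms by patient count, or by event count where only events are shown. Rate never sets the order.
- *That exposure-adjusted rates could not be obtained.* Total person-years are reported under SAP 13.1, so a crude rate can be worked out by hand for any row with an event count.
- *That SAP 13.4 prescribes the same faulty formula.* The sentence in 13.3 introduces the TEAE summaries and names Table 13-5. Tables 13-3 and 13-4 sit just before it in the same section under the same heading. For Table 13-6 the formula is only inferred from the column header; what can be said firmly is that the rate there is undefined.

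A further objection concerns the remedy: dividing everything by the 13.1 total would be wrong too. That total ends at last dose, while Protocol 8.1.3 collects adverse events to the last visit, which Protocol 6.2.9 places 28 to 35 days after discontinuation. The SAP's formal TEAE definition (13.3 and section 16) gives a start but no end, although a parenthesis in 13.3 limits such events to the treatment period. Nor is total exposure the right denominator for patients with a first event. This objection is correct, and the fix below allows for it.

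**Conclusion.** The definition is wrong as written. Followed literally, it yields a column labelled Rate that cannot exceed 1 on counts, is 1.0 for any event occurring once per affected patient, and drops to 0.25 when each affected patient has four events. This holds whether incidence is read as a number or a percentage, and it does not depend on the assumed 160 patients or on either exposure figure, which serve only as illustration.

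The defect is confined to the Rate column of Tables 13-3 to 13-5, with Table 13-6 left undefined. Incidence, event counts, exposure and all efficacy results are unaffected. It should be corrected because a reader who takes the heading at face value will be misled, and because correction is cheap.

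**What to change.** In SAP 13.3, replace the definition with number of events per 100 person-years, and state the same definition in 13.4 so that it governs Tables 13-3 to 13-6.

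Match numerator and denominator. Either count only on-treatment events against the SAP 13.1 exposure total, or extend person-time to cover the follow-up period in which events are still counted. Say which, and give the TEAE definition a matching end point.

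If a patient-based rate is also wanted, divide patients with the event by person-time to first event, censored at the end of the chosen window, and not by total exposure.

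The minimum acceptable change is to invert the ratio to events per affected patient and relabel the column, or to drop it. The inverted ratio moves the right way with recurrence, but it still does not show how many patients are affected (10 events in 10 patients and 80 in 80 both give 1), so the patient column must stay beside it.

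The cost is a few lines of SAP text. Events per 100 person-years needs little programming because the exposure total is already planned; extended person-time or time to first event needs a small amount more. No new data are required.

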Proportions of Patients and Eyes in the EAP with CRR from VA Nadir following 6 months and 12 months of treatment

CRR from Nadir	Patients		Eyes		Treatment duration at assessment [months]			
in the Efficacy Population	all	CRR	all	CRR	mean	(SD)	min	max
Patients with 6m assessment available	62	CRR at 6m 19 (30.6%)	124	CRR at 6m 30 (24.2%)	5.8	(1.0)	3.1	8.1
12m assessment available	47	CRR at 12m 17 (36.2%)	94	CRR at 12m 28 (29.8%)	11.6	(1.3)	9.1	13.9
at last observation	69	CRR at last obs. 34 (49.3%)	138	CRR at last obs. 55 (39.9%)	15.4	(9.0)	2.8	36.2

6m assessment : closest to 6 months, values at 3-9 months considered

12m assessment: closest to 12 months, values at 9-15months considered

Source Tables : EAP 01-01, EAP 01-02, EAP 01-03, EAP 02-01, EAP, 02-02, EAP 02-03

Magnitude of Recovery in Eyes in the EAP with CRR from VA Nadir at the 6 month, 12 month or at the last observation

Recovery* from Nadir [logMAR]**	N	mean	SD	median	max	min
at the 6 month vist	15	-0.47	0.31	-0.38	-1.00	-0.14
at the 12 month vist	15	-0.62	0.48	-0.40	-1.40	-0.10
at last observation (mean treat. dur. 20.9 m)	15	-0.93	0.42	-1.08	-1.44	-0.14

^{*}for eyes with CRR from BL where recovery had occured at the 6 months visit and a 12 month visit was available, too

Note, for these 15 eyes the VA at BL was also the VA at Nadir

Furthermore, data from the RHODOS and from the EAP provide evidence that the LHON-causative mutation harboured is prognostic of CRR in VA.

Therefore, secondary objectives of this study are to provide information on the effect of treatment duration on both the proportions of patients presenting with CRR and on the magnitude of any response with increasing treatment time and on the influence of the mutation harboured on CRR rate compared to spontaneous CRR (sCRR) untreated control patients.

The study will also allow the assessment of the safety and tolerability of long-term treatment with idebenone, with particular emphasis on the proportion of patients experiencing elevated Liver Function Tests (LFTs) or changes in blood cell counts.

^{**}off chart set to 1.70 [logMAR]

2 Study Objectives and Endpoints

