8.1.2 Adverse Events of Special Interest (AESI)

The detection, monitoring and evaluation of potential risks of idebenone are addressed in the idebenone risk management plan. AESI correspond to the important potential risks which are identified in the safety specification and listed in the Risk Management Plan and in the corresponding interface between the European Risk Management Plan and EudraVigilance. Important potential risks are important risks for which there is some basis for suspicion of a causal association with the medicinal product of interest but where this association has not been confirmed and needs further confirmed or rejected as new data on come available. Currently, there are no important identified risks, i.e. important risk for which there is adequate evidence of an association with the medicinal product of interest, listed in the idebenone RMP.

Therefore, particular attention should be paid to AESI that are described as follows as follows in this RMP and constitute important potential risks for idebenone:

- Abnormal liver function test (ALT, AST, total bilirubin, GGT) or hepatitis (liver disease)
- Blood count abnormalities (such as agranulocytosis, anaemia, leukocytopenia or thrombocytopenia)

In order to be considered as AESI, the events should in first place qualify as AE according to the guidance presented in 8.1.1 above.

Possible fluctuations of hepatic laboratory tests or blood count values which from medical history may be expected in the patient but which are not considered clinically relevant by the investigator should not be reported as AESI.

For hepatic laboratory tests listed above any change below 1.5XULN usually are considered not to be clinically relevant, but this qualification as not clinically relevant should always remain a judgment by the investigator in the individual patient.

For complete and accurate safety surveillance, the data collected on these pre-defined events will include as many details as possible to corroborate diagnosis.

AESI should be reported using the designated section of the SAE report form and transmitted to UBC with 24 hours of learning of its occurrence, regardless severity and seriousness assessment.

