9.4.3 Safety Evaluation

The disposition of the patients will be summarized by tabulating the number of enrolled, completed and discontinued patients. The reasons for premature discontinuations will be tabulated. The extent of exposure will be summarized by tabulating the duration of the study treatment.

All adverse events (AEs) will be coded using the MedDRA dictionary. The treatment-emergent AEs (i.e., events which start or worsen during the study treatment) will be tabulated by system organ class and preferred term. Both subject and event counts will be calculated. In addition, the treatment-emergent AEs will be evaluated by severity and by relationship to the study treatment. The serious AEs and AEs leading to a premature discontinuation will also be summarized.

The clinical laboratory variables and vital signs will be summarized descriptively, including a tabulation of normal and abnormal values.

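### SAP 13.3 reports related TEAEs by term as event shares and pools both AESI types in one row, so two useful patient counts are not shown directly

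*SAP*

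**What the plan says.** **SAP 13.3, default.** The TEAE summaries are introduced with "The incidence (number and % of patients), frequency (number of events) and rate (incidence/frequency) following summaries will be provided".

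**SAP 13.3, exception.** For "TEAEs broken down by SOC, PT and relationship to study medication", the rule is "event count only and % will be calculated out of the total number of TEAEs". The severity bullet carries the same rule. The sorting paragraph below Table 13-5 provides for tables that hold event counts only, so the choice looks deliberate.

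**Patient-level figures that the SAP does plan:**
- Table 13-3: patients and events by SOC and PT, any relationship.
- Table 13-4: patients with any AE, by severity, with any SAE, and with any AESI (one row).
- Table 13-5: patients with any drug-related TEAE, as one overall row, plus severe, serious, discontinuation, interruption and death rows.
- TEAEs leading to discontinuation, interruption or death, by SOC and PT.
- Table 13-6: patients per laboratory parameter, limited to out-of-range values that the investigator judged clinically significant.

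**Protocol.** Section 9.4.3 asks that "the treatment-emergent AEs will be evaluated by severity and by relationship to the study treatment". Section 8.1.2 lists two kinds of AESI: liver (abnormal liver tests or hepatitis) and blood count abnormalities. Section 1.2 describes the safety assessment as made "with particular emphasis on the proportion of patients experiencing elevated Liver Function Tests (LFTs) or changes in blood cell counts". Section 9.5 plans a count of patients with abnormal biochemistry, haematology and/or urine results, compared with Baseline.

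**The concern.** A share of all TEAEs is not a patient risk. Its denominator grows with unrelated events and with repeat events in the same patient, so the same related events print as a smaller percentage when the study records more of anything else.

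The pooled AESI row matters more. The protocol's emphasis is on the proportion of patients with liver-test or blood-count changes, whatever the cause. The natural summary is one total per type with each patient counted once. A patient with raised ALT, AST and GGT appears in three rows of Table 13-6 and may appear under several PTs in Table 13-3, so those rows cannot be added. Relatedness by term is the lesser loss, because it is an open-label investigator judgement with no comparator.

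**Working it through.** The documents give no figure on this point, so there is nothing to reproduce. The check is what a reader could recover from the specified tables. All event and patient counts below are assumptions. Only the denominator comes from the plan: 80 + 80 = 160 planned patients, all assumed to be dosed.

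**1. Patients with a related TEAE of one term**

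Inputs: E events in P patients (Table 13-3), R > 0 related events (relationship table), D patients with any drug-related TEAE (Table 13-5).

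- At most E − R patients can have only unrelated events, so the lower bound is max(1, P − (E − R)).
- The upper bound is min(P, R, D).
- This assumes that other terms hold enough related events that D does not raise the lower bound.

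Take E = 12, P = 8, R = 6. The lower bound is 8 − (12 − 6) = 2 and the upper bound is min(8, 6, D).

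| D | Related patients | % of 160 |
|---|---|---|
| 6 or more | 2 to 6 | 1.25 to 3.75 |
| 4 | 2 to 4 | 1.25 to 2.5 |
| 2 | exactly 2 | 1.25 |

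The planned table would print 6/500 = 1.2% if there were 500 TEAEs, and 6/1,000 = 0.6% if there were 1,000. Neither is a patient percentage.

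The bounds meet in several ordinary cases:
- No patient repeats the term (E = P): both bounds equal R. With P = 6 and R = 4, the lower bound is 6 − 2 = 4 and the upper bound is 4.
- All events of the term are related: both bounds equal P.
- R = 1 or P = 1: exactly 1. If R = 0, the answer is 0.

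The gap therefore opens for terms with repeat events of mixed causality.

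**2. Patients by AESI type, any cause**

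Suppose four liver PTs have 2 patients each, two blood-count PTs have 1 patient each, and Table 13-4 shows A = 6 AESI patients. Assume these PTs are exactly the AESIs.

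- Liver patients L lie between 2 (complete overlap) and 2 + 2 + 2 + 2 = 8 (none). Blood-count patients B lie between 1 and 2.
- The pooled row requires max(L, B) ≤ A ≤ L + B. So L is at least max(2, 6 − 2) = 4 and at most min(8, 6) = 6.
- Result: 4 to 6 patients, or 2.5% to 3.75% of 160.
- With no blood-count AESI, L is exactly 6. From the pooled row alone, without PT counts, L could be anything from 0 to 6.

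A SOC-level patient count in Table 13-3 can narrow this when all terms of a type fall in one SOC. The PT counts help only as far as events of those PTs were reported as AESIs. Protocol 8.1.2 leaves that to the investigator's judgement of clinical relevance, event by event.

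**3. Related liver AESIs**

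One related event in each of the four liver PTs, all AESI-flagged, gives one related patient per PT. The union is 1 to min(4, A, D): 1 to 4 patients (0.6% to 2.5%) if D is 4 or more, and 1 to 3 (0.6% to 1.9%) if D = 3.

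**The case against.** The best defence is that this is preference. Protocol 9.4.3 asks for subject and event counts by SOC and PT, and for TEAEs to be evaluated by relationship, and the SAP does both. Nothing in either document requires patient counts by term and relatedness, or AESI totals by type. The emphasis in Protocol 1.2 concerns laboratory changes, and Table 13-6 gives patient counts for each liver and blood-count parameter. The examples are constructed, and the exact 95% intervals for 2/160 (0.15% to 4.44%) and 6/160 (1.39% to 7.98%) overlap widely. Section 9 of the SAP also promises a listing of LEROS data, from which patients might be counted by hand.

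Much of this stands. A reader might infer that the SAP breaches the protocol, that no patient-level safety data are planned on relatedness or on liver and blood findings, or that the missing counts can never be recovered. The documents support none of these: the protocol wording is met, Tables 13-3 to 13-6 are patient-level, and sparse terms resolve exactly.

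Some of it does not stand:
- Table 13-6 is per parameter and limited to clinically significant values, so it gives no total per type.
- The SAP specifies no table for the patient count planned in Protocol 9.5, and that count does not clearly separate liver from other biochemistry.
- SAP 13.3 names no AE listing, while 13.2 and 13.4 to 13.7 each name their own. Counting by hand is in any case no substitute for a table.
- Overlapping intervals describe sampling error. The gap here is different: the database holds the exact count and the table leaves it out.

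**Conclusion.** Minor, and confined to reporting. The specified tables do not directly show patient n (%) with a related TEAE by term, or patient n (%) by AESI type counted once per patient. The second is the main loss, because it is closest to the protocol's stated safety emphasis.

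The size depends on the data. It is nil where terms do not repeat within patients or only one AESI type occurs. In the assumed examples it is an uncertainty of 2 to 6 patients for a term and 4 to 6 for liver AESIs, out of 160. The conclusion covers the tables named in SAP section 13; an unspecified listing with relationship and AESI flag would let a reader count by hand. Efficacy results and the planned all-causality tables do not change.

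**What to change.** **1. Table 13-4.** Split the AESI row into liver and blood count, each overall and drug-related. Give patient n (% of the Safety population), counting each patient once per type, plus events. Assign to a type only events flagged as AESI, not every event of a PT, using a short mapping of terms to type fixed before database lock. The flag should be available, since Protocol 8.1.2 says "AESI should be reported using the designated section of the SAE report form".

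**2. Relationship bullet of SAP 13.3.** Replace the event-only rule with: patients with at least one related TEAE (n and % of the Safety population) and number of events, by SOC and PT; one related event of a term makes the patient related for that term.

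**Optional.** The severity bullet could take the same wording, with each patient counted at worst severity.

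**Cost.** Revised SAP wording, about four rows in Table 13-4, patient columns in the relationship table and the mapping list. Relationship is already recorded for each AE (Protocol 8.1.4 and 8.1.6), so no new data are needed.
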